7.2 Timing of Analyses

All final, planned analyses identified in this SAP will be performed only after the last participant has completed the Month 24 study visit and all relevant study data have been processed and integrated into the analysis database. In addition, no database may be locked or analyses completed until this SAP has been approved.

7.3 Populations

Assignment of participants to Populations will be done prior to the final data lock for the study. The following Populations will be defined: Population modified Intent to Treat (mITT) Set, Per Protocol Population Set, and Safety Population Set.

The analysis of baseline characteristics and efficacy endpoints will be performed on the mITT Population Set as defined below in Section 7.3.1. The primary efficacy analysis will also be performed on the Per Protocol Set as an additional sensitivity analysis. All safety analyses will be performed on the Safety Set.

7.3.1 Modified Intent-to-Treat Population

The Population mITT Set will include all randomized participants who received surgery (NT-501 implant or sham surgery) whether or not the participant adhered to the study protocol. Participants will be analyzed according to the treatment group to which they were randomized. All analyses of efficacy and non-safety (e.g., demographics) parameters will reference the mITT Population, as appropriate.

7.3.2 Per Protocol Population

The Per Protocol (PP) Population will be a subset of the mITT Population and will include all available data from participants who follow the protocol without major protocol violations(s). Major protocol violations are defined as deviations that may have a substantial impact on efficacy assessments. The criteria to be used for excluding participants from the PPS will be determined and documented before the final database lock. Participants will be analyzed according to the treatment group to which they were randomized. The PP Population will be used to perform supportive analyses of the primary and secondary endpoints.

7.3.3 Safety Set

The Safety Population will be defined as all participants who were randomized and received surgery (NT-501 implant or sham surgery) and have at least 1 safety measurement. Participants will be analyzed according to the group according to the treatment received, and no participants (or data) will be excluded from this dataset because of protocol violations that occur during the study. All analyses of safety will be conducted using the Safety Set.

7.3.4 Other Sets

Not applicable.

7.4 Covariates and Subgroups

There are no plans to adjust the primary efficacy analysis for baseline characteristics and disease status. Exploratory analyses will be conducted to assess the potential contribution of baseline disease characteristics on the likelihood of a response to treatment.

Exploratory analyses will be performed to assess the potential impact of various prognostic factors on efficacy. Appropriate statistical models will be fit with these factors as covariates and the effect of treatment will be assessed after adjusting for other significant risk factors. Risk factors will include, but are not limited to age, gender, region, and baseline EZ area.

7.5 Out of Window Visits for Primary and Secondary Variables

Every effort will be made to keep missing data at a minimum. Due to COVID-19, participants may not be able to attend their scheduled study visits within the protocol-specified visit window (+/- 30 days). To accommodate such delays, efficacy assessment visits delayed due to COVID-19 but conducted within -30 days of Month 12 visit or +119 days of the planned visit timepoints for Months 12, 16, 20, and 24 will be included in the analysis. To account for the variable timing of visits, the relative study day of assessments will be included in regression models as a continuous measure of Time where relative study day is defined as the number of days since surgery.

If time is included as a categorical variable (see Section 7.6), an estimated value for the scheduled visit endpoint will be computed from the raw data, adjusting the observed value to an estimated value at the targeted visit time, based on a linear trend since the previous observation. The estimated value for a participant-visit will be computed by determining the linear slope between the previous visit and the current visit. The estimated value will be the fitted value to that line at the targeted timepoint.

7.6 Interim Analyses

No formal interim analyses or early unmasking are planned.

Prior to the completion of the study and database lock, summaries of the distribution of timing of efficacy visits (excluding any efficacy variables themselves) will be compared between treatment arms to determine if the pattern of visit attendance is comparable between treatment arms.

In addition, masked summaries of the overall results will be analyzed to determine appropriate parameterization of time as a continuous or categorical variable for the primary efficacy analysis. The determination of non-linearity will be concluded if the observed pattern of EZ area loss response over time follows a distinctly non-linear trend. Assessment will be made through an overall linear regression goodness-of-fit analysis, including review of a residual plot from a simple linear regression.

The analysis will be limited in scope and will not reveal unmasked results. No type I error adjustment will be made.

7.7 Data and Safety Monitoring Committee

An independent DSMC will be established to monitor safety and the study conduct and will meet to review masked safety summaries prepared by the Coordinating Center. Members of the DSMC are external to the Sponsor and will follow a charter that outlines its roles and responsibilities. No interim analysis for efficacy is planned for this study.

The DSMC will review accumulating data for safety per the DSMC Charter. The DSMC will be responsible for monitoring data and safety and will exercise oversight of the clinical investigation independently from the study investigators. In addition, the DSMC will be responsible for reviewing the study design and, as appropriate, recommending safety design changes. More details on the DSMC role and responsibility for data monitoring can be found in the Charter.

Participants will be monitored during all study visits for AEs by the study investigators. The investigator will be responsible for the appropriate medical management of all AEs and for the personal safety and well-being of the participants. In case of an AE, the clinical investigator will initiate appropriate treatment per his/her medical judgment and will decide whether to continue treatment through full resolution of the event, discontinue the IP, or withdraw the participant from the study.

Regardless of severity or relationship to the IP, all AEs occurring during the study will be recorded in the participant's CRF. Any SAE will be reported immediately by entering the data into the EDC system within 24 hours of the investigator becoming aware of the occurrence of a serious or unexpected AE. This will notify the Coordinating Center which in turn will notify the Sponsor.

7.8 Multiple Comparisons/Multiplicity

The primary efficacy analysis involves a single hypothesis test at the 2-sided significance level of 5%. A hierarchical testing procedure will be applied to secondary efficacy analyses to control the overall type I error rate. In the case that the primary efficacy analysis is statistically significant, the secondary efficacy endpoints will be tested at a 2-sided type I error rate of 0.05 in the order listed below. If any of the secondary endpoints are found to be not statistically significant at the 2-sided 0.05 level, the hypothesis testing will stop. Later endpoint(s) will be summarized descriptively and p-values may be produced for descriptive purposes only.

- Mean change in aggregate sensitivity of microperimetry within the EZ line break area from the Baseline Visit through the Month 24 Visit
- Mean change in reading speed from the Baseline Visit through the Month 24 Visit

- Mean change in the National Eye Institute Visual Function Questionnaire-25 (NEI-VFQ-25) near activities subscale score from the Baseline Visit through the Month 24 Visit

P-values produced for safety analyses and treatment group comparisons of demographic and baseline characteristics will be considered descriptive statistics that support the results of the primary efficacy analysis and not as formal tests of hypotheses.

8 STUDY PARTICIPANTS

8.1 Disposition of Participants

Number and percentage of participants in the following categories will be summarized as appropriate:

- Randomized and received surgery (FAS)
- Randomized, Received Surgery and at least one safety measurement (Safety Set)
- Included in the PPS
- Prematurely discontinued in the study during the Treatment or Extension Periods and the reasons for discontinuations

A time to premature discontinuation analysis using the Kaplan-Meier method will be provided to assess the comparability of treatment groups in terms of premature discontinuation.

The disposition summary and discontinuation analysis will be based on the mITT Population.

8.1 Demographics and Baseline Characteristics

Demographic and ocular baseline characteristics (e.g., baseline EZ area) will be summarized. The demographics and baseline characteristics will be presented for both the mITT Population and the PP Population to allow review of characteristics of those included in the efficacy analysis, which will be based on these populations.

The medical and ophthalmic history data will be collected at the baseline visit including:

- Ongoing medical conditions
- Ocular history, ongoing ocular history, and confirmation of MacTel

Medical and ophthalmic history conditions will not be coded using the Medical Dictionary for Regulatory Activities (MedDRA). Therefore, there will be no summary table, but all conditions will be provided in a participant listing for the FAS only.

8.2 Protocol Deviations

Protocol deviations will be provided as a participant data listing only. Major protocol violations will also be identified for analysis purposes.

8.2.1 Prior and Concomitant Medications

Frequency distributions and listings of concomitant medications will be shown by Anatomical Therapeutic Chemical (ATC) drug classification, drug name and treatment group. The medications will be shown separately for those starting before and after implant/sham surgery. All concomitant medications will be coded using the World Health Organization Drug Dictionary (WHO-DD). Prior and

concomitant medications will be summarized for the Safety population.

If medication start date is on or after date of dosing of study drug, then medication will be summarized as a concomitant medication regardless of whether medication end date is missing or not. If medication end date is before date of surgery, then medication will be summarized as prior medication regardless of whether medication start date is missing or not. Note that medication that started prior to surgery and continued after surgery will be summarized as prior medication and separately as a concomitant medication. Both prior and concomitant medications will be based on the FAS. If the data contain missing or partial medication start and stop dates which do not allow definitive classification as either a prior medication, concomitant medication, or both, a conservative rule will be implemented. This will be detailed in the statistical programming document for the study.

8.2.2 IP Exposure

IP for this study is the NT-501 implant that remains in place for the duration of the study, therefore the participant is not responsible for administering IP. An analysis of IP compliance is not measured, yet information will be provided on the number and percentage of participants based on the mITT Population who have the device removed during the study period.

9 EFFICACY EVALUATION

9.1 Primary Efficacy Analysis

The primary hypothesis is that the NT-501 implant will slow the rate of change in the EZ (IS/OS) area loss. The primary efficacy endpoint will be analyzed using the mITT Population but restricted to only those participants with at least 3 visits recorded: Baseline, Month 24, and at least one of Month 12, 16, or 20 visits. An analysis will also be conducted with the PP Population with the same restriction to only participants with at least 3 visits recorded: Baseline, Month 24, and at least one of Month 12, 16, or 20 visits.

The primary efficacy variable will be the rate of change that will be determined by using values from the EZ area as measured by SD-OCT. EZ area will be defined as the mean of 2 independent readings of the single eligible SD-OCT enface image taken at Baseline and at Months 12, 16, 20, and 24. A longitudinal mixed model will include EZ area as the dependent variable, a random intercept term to account for within subject variability, treatment group, time as a continuous variable, and the interaction between treatment and time. Time will be captured as the relative study day of the respective efficacy assessment and will include the days corresponding to the Baseline, Month 12, 16, 20, and 24 visits. The difference in the rate of change in EZ area over 24 months will be computed by including Baseline, Months 12, 16, 20, and 24 EZ measurements, will be compared using a random intercept model and the corresponding 95% confidence interval (CI), SE, test statistic, and 2-sided p-value of the difference between treatment group parameters by computing the parameter estimate for the treatment by time interaction term. An unstructured covariance structure will be implemented as with continuous time there will be a single parameter each for between and within participant variability.

Prior to the analysis, out of window visits will be incorporated as noted in Section 7.5. With a mixed effects model as the primary analysis model, no imputation of missing data will be done.

As stated in Section 7.6, it may be determined prior to study end and database lock that the most appropriate parameterization of time is as a categorical variable. If this occurs, the modification to the

above plan will be documented ahead of analysis. The model will proceed as described above with the exception that time will be included in the model with nominal visit labels for Months 12, 16, 20, and 24. The comparison between treatment groups will be assessed at Month 24. The preferred covariance structure is Unstructured. If the model does not converge, the covariance structure will be selected from one of the following: Variance Component, Compound Symmetry, or Auto-regressive covariance matrix through comparison of the Akaike Information Criterion [17].

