12. STATISTICS

12.1 GENERAL PROCEDURES

This is a Phase 3 study to evaluate the efficacy and safety of NT-501 compared with the sham procedure for the treatment of MacTel.

One eligible study eye from each participant will be randomized in a 1:1 ratio as follows:

- Surgery to receive 1 NT-501 device implant delivering a nominal CNTF dose of 20 ng/device/day
- Sham surgery

Randomization: Two treatment assignments with a 1:1 (NT-501 surgery: sham procedure) allocation scheme for each of the 2 protocols (Protocol A and Protocol B). The actual treatment assignment (NT-501 surgery or sham procedure) will be shown within Advantage eClinical. Randomization is unrestricted. One randomization list per protocol will be generated. There will be no stratification for prognostic factors.

The biostatistician will prepare detailed statistical procedures, listings, table shells and figures in a separate statistical analysis plan (SAP). The following key components will be considered, and a detailed description will be documented in the SAP:

- Descriptions of primary and secondary endpoints and how they will be measured
- Statistical methods and any applicable alternative methods (eg, model nonconvergence) used to analyze the endpoints
- Justifications for sample size calculations
- Multiple testing approaches
- Approaches to account for missing data

A biostatistician will perform statistical analyses as agreed with the sponsor according to the SAP. Any additional or supplemental data analyses performed independently by an investigator shall be submitted to the sponsor for review.

Analysis Populations:

The modified intention-to-treat (mITT) population will consist of all randomized participants who received surgery (NT-501 or sham surgery), all of whom will be analyzed in the treatment group to which they were assigned regardless of compliance or other protocol deviations.

The per-protocol (PP) population will be a subset of the mITT population and will include all available data from participants who follow the protocol without major protocol deviation. The PP population will be used for analyses of primary and key secondary efficacy variables. Participants will be analyzed according to the randomized treatment. The determination of all protocol violations and any data excluded from the efficacy analysis will be made prior to locking the final database.

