As the efficacy endpoints in this study are longitudinal, measured over the course of multiple observations over time, the minimum requirement for completion of the study is to have measurements at Baseline and Month 24, plus at least one interim visit for the primary efficacy endpoint. Imputation methods may be implemented for sensitivity assessments of primary and secondary efficacy analyses should the dropout rate and proportion of missing values be higher than expected or should there be missing data due to an identifiable cause unrelated to study procedures or treatments (e.g. delayed visits due to COVID-19).

Covariates and Subgroups:

There are no plans to adjust the primary efficacy analysis for baseline characteristics and disease status. Exploratory analyses will be conducted to assess the potential contribution of a number of baseline disease characteristics as well as study site on the likelihood of a response to treatment.

Exploratory analyses will be performed to assess the potential impact of various prognostic factors on efficacy. Appropriate statistical models will be fit with these factors as covariates and the effect of treatment will be assessed after adjusting for other significant risk factors. Risk factors will include, but are not limited to age, race, sex, and baseline EZ area.

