12.3 STATISTICAL METHODS

12.3.1 Primary Endpoint(s)

The primary hypothesis is that NT-501 will slow the rate of change in the EZ (IS/OS) area loss. The primary efficacy endpoint will be analyzed using the mITT population (main analysis) but restricted to only those participants with at least 3 visits recorded. Baseline, Month 24, and at least one of Month 12, 16, or 20. A similar analysis will also be conducted with the PP Population.

The primary efficacy variable will be the rate of change that will be determined by using values from the EZ area as measured by SD-OCT. EZ area will be defined as the mean of 2 independent readings of the single eligible SD-OCT enface image taken at baseline and Months 12, 16, 20, and 24. A longitudinal mixed model will include EZ area as the dependent variable, a random intercept term to account for within subject variability, treatment group, time as a continuous variable, and the interaction between treatment and time. Time will be captured as the relative study day (defined as days since date of surgery) of the respective efficacy assessment and will include the days corresponding to the Baseline, Month 12, 16, 20, and 24 visits. The difference in the rate of change in EZ area over 24 months (to be computed by including baseline and Months 12, 16, 20, and 24 EZ measurements) will be compared using a random intercept model and the corresponding 95% confidence interval (CI), SE, test statistic, and p-value of the difference between treatment group parameters by computing the parameter estimate for the treatment by time interaction term. An Unstructured covariance structure will be implemented as with continuous time there will be a single parameter each for between and within participant variability.

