18. STUDY DISCONTINUATION

Both the sponsor and the principal investigator reserve the right to terminate the study at the investigator's site at any time. Should this be necessary, the sponsor or a specified designee will inform the appropriate regulatory authorities of the termination of the study and the reasons for its termination, and the principal investigator will inform the IRB/IEC of the same. If the decision is made to terminate the study, the sponsor and the principal investigator will assure that adequate consideration is given to the protection of the participants' interests.

The investigator may discontinue a participant from the study if warranted. The investigator and the sponsor may also request the withdrawal of a participant because of noncompliance (eg, missed visits), administrative reasons, or any other valid and ethical reasons.

Reasons for participant discontinuation may include, but are not limited to, the following:

- Investigator determination that it is not in the best interest of the participant to continue participation
- Intercurrent illness
- AE that is serious and unexpected
- Worsening condition
- Any other safety concerns

If a participant withdraws or is discontinued from the study before the Month-24 Visit, they should return for an exit visit. The schedule of assessments for this visit is the same as that for the 24 month.

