value. These definitions will apply to all analysis variables: demographics, background, baseline characteristics, efficacy and safety, unless otherwise specified.

Unscheduled measurements will be recorded as such and not attributed to a scheduled measurement time point, unless otherwise specified. Where applicable, visit windows for efficacy analysis are presented in the relevant section.

Incomplete/Missing data: Missing post-baseline values will not be imputed for the primary efficacy analysis conducted using longitudinal mixed effects methods, which make use of all available data even if a participant has missing data at some post-baseline visits. For some endpoints, sensitivity analysis including imputation may be conducted. Where applicable, these analyses have been indicated in Section 9.1.1.

For safety analysis, no imputation will be used. Missing data (e.g., dates) will remain as missing, and conservative conventions established, as required. These will be documented in the statistical programming document for this study.

No formal statistical analyses will be performed to detect and/or remedy the presence of statistical outliers.

Measurements recorded more than once at a certain time point are defined as replicate observations. If a measurement is replicated and both are valid, the first recorded measurement will be used for analysis. Replicated measurements are expected for the baseline MAIA.

Measurements recorded for the same participant at different time points are defined as repeated observations. If an assessment has planned repeated measurements, then statistical summaries will present all planned time points, as appropriate (e.g., EZ area loss).

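### The confirmatory EZ analysis keeps only participants with Baseline, Month 24 and an interim visit, so it discards usable data and selects on attendance after randomisation

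*SAP*

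**What the plan says.** SAP 9.1 has the primary endpoint "analyzed using the mITT Population but restricted to only those participants with at least 3 visits recorded", and then names Baseline, Month 24 and one or more of Months 12, 16 and 20. Protocol 12.3.1 gives the main mITT analysis the same limit: "but restricted to only those participants with at least 3 visits recorded". Protocol 12.1 uses this pattern, without naming the interim months, as its definition of a completer: "the minimum requirement for completion of the study is to have measurements at Baseline and Month 24, plus at least one interim visit". SAP 9.1 applies the restriction to the PP analysis as well.

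The population definitions carry no attendance condition. Under Protocol 12.1 the mITT population is everyone randomised and operated on, "all of whom will be analyzed in the treatment group to which they were assigned regardless of compliance or other protocol deviations". SAP 7.3.1 includes them "whether or not the participant adhered to the study protocol". SAP 7.1 justifies not imputing by pointing to mixed models, "which make use of all available data even if a participant has missing data at some post-baseline visits", and SAP 9.1 repeats that reason.

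Participants who leave before Month 24 are covered in Protocol 18: "they should return for an exit visit. The schedule of assessments for this visit is the same as that for the 24 month". Neither document says whether the EZ value from that visit counts as Month 24 or enters the model. The nearest rule is in SAP 7.1: "Unscheduled measurements will be recorded as such and not attributed to a scheduled measurement time point, unless otherwise specified".

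SAP 9.1.1 lists a sensitivity analysis headed Inclusion of all participants. Its one sentence speaks of assessment timing and does not mention the 3-visit rule.

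**The concern.** Month 24 and interim attendance both happen after randomisation. Conditioning the confirmatory comparison on them means that the two groups compared are no longer the randomised groups. The plan justifies not imputing by saying that the mixed model uses all available data. That holds for gaps within the restricted set, but not for participants removed outright.

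Two things are at stake.

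- **Information.** A participant with Baseline, 12, 16 and 20 but no Month 24 contributes nothing, although three post-baseline readings exist. Such gaps are foreseeable. SAP 6.1 reports a marked rise in missed and out-of-window visits from COVID-19, and Protocol 6.1 has a delayed visit skipped if it cannot be done within 119 days.
- **Bias.** Protocol 18 lists a worsening condition among the reasons for discontinuation. If fast progressors leave one arm more than the other, that arm's remaining participants look slower. Loss from NT-501 would flatter the implant, and loss from sham would hide a benefit.

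The primary p-value opens the hierarchy for the three secondary endpoints (SAP 7.8), so the choice of analysis set affects those tests too.

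**Working it through.** **Inputs (Protocol 12.2, SAP 5).** σ² = 0.0256, ρ = 0.6, s_x² = 0.47, n = 5 (Baseline, 12, 16, 20, 24 months), d = 0.037 mm²/year, two-sided α = 0.05, 80% power, 50 per arm raised to 56.

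**The plan's own figure.** m = 2(1.960 + 0.842)² × 0.0256 × 0.4 / (5 × 0.47 × 0.037²) = 49.97, so 50 per arm. It reproduces. The step from 50 to 56 allows for 1 − 50/56 = 10.7% not evaluable, which is 6 per arm.

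**Slope information held by each visit pattern.** In the random-intercept model, within-participant information on slope is proportional to Σ(t − t̄)², with t in years.

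| Visits with EZ | Σ(t − t̄)² | Share of full record | Under the rule |
|---|---|---|---|
| 0, 12, 16, 20, 24 | 2.356 | 100% | kept |
| 0, 12, 24 | 2.000 | 85% | kept |
| 0, 24 | 2.000 | 85% | dropped |
| 0, 12, 16, 20 | 1.556 | 66% | dropped |
| 0, 12, 16 | 0.963 | 41% | dropped |
| 0, 12 | 0.500 | 21% | dropped |

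The rule does not follow information. Month 12 is the midpoint of 0 and 24, so adding it leaves Σ(t − t̄)² at 2.000, yet it decides whether the participant is in or out.

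**Power when loss is unrelated to outcome.** The documents give no exclusion rate, so the counts are assumed. For the restricted test, SE = √[2σ²(1 − ρ)/(kept per arm × 2.356)]. With 50 kept, SE = √[0.02048/117.8] = 0.01319, and power = Φ(0.037/0.01319 − 1.96) = 80.1%. The all-data figures use generalised least squares for the same model. This adds a little between-participant information to the within-participant sum.

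| Lost per arm | Restricted | All data: 0,12 | 0,12,16 | 0,12,16,20 | 0,24 |
|---|---|---|---|---|---|
| 6 of 56 | 80.1% | 81.5% | 82.1% | 83.1% | 83.8% |
| 11 of 56 | 75.9% | 78.7% | 80.0% | 81.9% | 83.3% |

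With 7 lost per arm, the restricted test falls to 79.3%.

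**Bias when loss depends on progression (simulation).** The model was a random-intercept REML fit with treatment by time, 56 per arm, and loss after Month 12 in one arm. The loss mechanisms are assumed. With 8,000 runs, the Monte Carlo SE is 0.0001 on bias and about 0.24 points on a 5% rate (√[0.05 × 0.95/8000]). There is no true effect in these rows. Bias is in mm²/year and is shown as a size.

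| Loss rule (observed Month 12 change) | Bias: restricted / all data | Two-sided rejection: restricted / all data |
|---|---|---|
| Log-odds 1 per SD, 5% lost | 0.0016 / 0.0001 | 5.6% / 5.3% |
| Log-odds 1 per SD, 10.7% lost | 0.0029 / 0.0001 | 5.9% / 5.1% |
| Log-odds 1 per SD, 15% lost | 0.0039 / 0.0002 | 6.2% / 5.1% |
| Log-odds 0.5 per SD | 0.0017 / 0.0001 | 4.9% / 4.7% |
| Log-odds 1.5 per SD | 0.0040 / 0.0000 | 6.2% / 5.3% |
| Six largest increases all leave | 0.0061 / 0.0000 | 8.1% / 5.0% |

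With a true effect of 0.037 and the log-odds 1 rule acting in sham, power is 75.9% restricted and 83.4% with all data. When the same rule acts in both arms with no effect, bias is 0.0001 either way (5,000 runs).

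A harsher assumption has 6 per arm miss Month 24 according to observed Month 20 change, in opposite directions in the two arms. It gives bias of about 0.012 and 11.7% rejection restricted, against 0.001 and 5.8% with all data (600 runs, SE about 1 point).

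**Where all data help less.** If true slopes vary between participants (assumed SD 0.05 or 0.10; 5,000 runs, SE 0.0002 to 0.0003):

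- Loss on observed Month 12 change: 0.0046 falls to 0.0015 (SD 0.05), and 0.0084 to 0.0050 (SD 0.10). That removes 67% and about 40%.
- Loss on true slope, last visit Month 12: 0.0049 to 0.0041, and 0.0095 to 0.0078. That removes 16% to 18%.
- The same with an exit reading at Month 14 entered: 0.0035 and 0.0066. About 30% is removed.
- Loss on true slope with last visit Month 20 (SD 0.10): 0.0092 to 0.0030. About two thirds is removed.

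**The case against.** The rule is prespecified and identical in both documents, and the plan has safeguards.

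- The increase from 50 to 56 per arm is there to protect power in the evaluable population, and 6 exclusions per arm leave the restricted test at its 80% target.
- Protocol 12.4 and SAP 7.6 compare visit-attendance patterns between arms before lock. SAP 8.1 adds a Kaplan-Meier comparison of discontinuation.
- Protocol 18.1 expects few discontinuations and keeps participants in follow-up after device removal. Protocol 12.1 allows imputation-based sensitivity analyses if dropout is higher than expected.
- The all-participants sensitivity analysis would, on its natural reading, restore those dropped.
- With the COVID windows, Months 12, 16 and 20 cover days 330 to 719 without a gap. Baseline plus Month 24 alone should therefore be rare, and missing one or two interim visits excludes nobody.
- The bias figures rest on assumed mechanisms, and most are small.

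Much of this stands as to size. Leaving out the Baseline plus Month 24 pattern, the gain at 6 lost per arm is 1.4 to 3.0 points. In the milder bias scenarios the difference in rejection rate is close to simulation error.

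None of it changes who enters the confirmatory test. The attendance and Kaplan-Meier comparisons can reveal a difference between arms but carry no rule for acting on it. SAP 9.1.1 lists no imputation analysis. A sensitivity analysis cannot alter the p-value that opens the hierarchy, and this one does not say that it lifts the 3-visit rule.

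**Conclusion.** The concern holds. The primary analysis is a completers analysis that selects on post-randomisation attendance and discards EZ values its own model could use. The likeliest cost is information: about 1 to 4 points of power at 6 lost per arm, and about 3 to 7 points at 11 lost per arm. Both counts are assumptions, since the documents give no rate.

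Bias is a conditional risk. There is none if loss is unrelated to outcome, or follows the same rule in both arms under no effect. With one-arm loss driven by observed progression, the main case gives 0.0029 mm²/year (8% of 0.037), and the extreme case gives 0.0061 (16%). Using all data removes nearly all of this if the random-intercept model holds, and less if true slopes differ between participants. In every one-arm progression-dependent scenario run, the all-data bias was the smaller. This should be fixed before lock, though it does not by itself undermine the design.

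**What to change.** 1. In SAP 9.1 and Protocol 12.3.1, state that the primary model uses all mITT participants and every observed in-window EZ value at Baseline and Months 12, 16, 20 and 24, with no minimum-visit rule.
2. Make the 3-visit set a sensitivity analysis. Say whether the PP analysis keeps the restriction, and leave the completion rule in Protocol 12.1 as a disposition term only.
3. In SAP 9.1.1, state that the all-participants analysis lifts the 3-visit rule as well as the timing limits.
4. State that EZ values from the early-withdrawal exit visit enter the model at their actual study day, as an explicit exception to the visit windows and to the SAP 7.1 rule on unscheduled measurements.

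The cost is a few sentences and a swap of the primary and sensitivity sets. No new data, visits or participants are needed. SAP 1 allows amendment until database lock. The change to Protocol 12.3.1 has to go through the formal amendment process in Protocol 16, including ethics committee and regulatory submission.
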